The results of this study will provide important information regarding two non-pharmacologic, evidence-based interventions (CBT and tDCS), and will help inform policies and programs to better serve the needs of U.S. military personnel, Veterans, and their families. The proposed study will also help elucidate the mechanisms underlying improved outcomes. The findings from this study may help reduce public health expenditures and morbidity/mortality associated with chronic pain and co-morbid prescription opioid use disorders, improve military readiness, and improve patient care provided in the military healthcare system.

Risk Benefit Ratio

As discussed above, our research team will attempt to maximize potential benefits and minimize potential risks. Knowledge gained by the proposed study will help address the immediate need for empirical evidence regarding optimal, non-pharmacologic treatments for Veterans and their family members with chronic pain and comorbid prescription opioid use disorders. Should new information that would affect the risk-benefit ratio become available during the course of the trial, subjects will be notified and modifications made in consultation with the Data and Safety Monitoring Board (DSMB).

Data and Safety Monitoring (DSM) Plan

This section is based on the recommendations in NIDA's "Guidelines for Developing a Data and Safety Monitoring Plan" (www.drugabuse.gov/funding/dsmbssop.html).

Summary of the Protocol. This application proposes to test the feasibility and preliminary efficacy of tDCS in combination with CBT to improve sleep, and reduce pain and severity of prescription opiate use disorders among Veterans and their family members with chronic pain and co-morbid prescription opioid use disorders. The primary outcome of interest includes reduction in pain and opioid use severity, and improve sleep.

Trial Management. The study will be primarily managed from the Brain Stimulation Lab ([name], Contact PI) within the Department of Psychiatry and Behavioral Sciences at the Medical University of South Carolina. The target population is described above in the inclusion/exclusion criteria.

Data Management and Analysis. A detailed data analysis plan is outlined in the Statistical Analysis and Power section. Primary outcomes include pain (BPI, daily diary ratings), opioid use severity (COMM, TLFB), and sleep (actigraphy sleep measures). Analyses will be guided by the specific hypotheses of the study. Post-hoc exploratory analyses will be conducted with two-tailed tests and more conservative statistical procedures which guard against Type I error (e.g., Tukey tests). All primary hypotheses will be tested at level of significance $\alpha=0.05$. We will also estimate the effect sizes of interest and provide 95% confidence intervals for them. See the Statistical Analysis and Power section for more details.

Quality Assurance. Data quality will be monitored by random inspection of the completed forms by research staff and any irregularities or problems detected will be discussed with the PI. Study therapists will receive standardized training from the PI and [name] (Consultant on this project) who develop the CBT intervention to be utilized in the proposed study. Adherence to the manual will be monitored using videotapes and weekly supervision. If therapy drift is observed the therapists will be re-trained. Booster sessions will be held annually.

Regulatory Issues. All unexpected Adverse Events (AEs) will be reported to the MUSC IRB within 10 working days. Serious AEs (SAEs) will be reported within 24-business hours. Follow-up of all unexpected and serious AEs will also be reported to these agencies. All AEs are reviewed weekly by the PI, bi-annually by the Data Safety Monitoring Board (DSMB) and yearly by the IRB. Any significant actions taken by the local IRB and protocol changes will be relayed to NIH. AEs and SAEs occurring during the course of the trial will be collected, documented, and reported in accordance with protocol and IRB reporting requirements. All research staff involved with adverse event reporting will receive general and protocol specific AE/SAE training including identification, assessment and evaluation, and documentation and reporting. The Study Coordinator, Research Assistant or Study Therapists will identify any potential AEs during the course of the study from subject self-report and administration of assessments and procedures. This information will be provided to the Study Physician ([name]), who will be responsible for AE/SAE assessment and evaluation including a determination of seriousness and study relatedness.

Definition of AE and SAE. Adverse events are defined as any untoward medical occurrence that may present itself during treatment or administration of an intervention, and which may or may not have a causal relationship with the treatment. Serious adverse events are defined as any medical occurrence that:

- Results in death,
- Is life-threatening,
- Requires inpatient hospitalization or prolongation of existing hospitalization,
- Results in persistent or significant disability/incapacity,
- Is a congenital anomaly/birth defect.

OR

- Requires intervention to prevent one of the above outcomes.

Documentation and Reporting. AEs/SAEs are documented and reported as per protocol and IRB requirements. Research staff will identify adverse events and obtain all available information to assess severity, seriousness, study relatedness, expectedness, outcome and the need for change or discontinuation in the study intervention. Adverse events are generally documented on AE Logs and AE Case Report Forms (CRFs). Additional relevant AE information if available should be documented in a progress note in the research record as appropriate to allow monitoring and evaluating of the AE. If the AE meets the definition for serious, appropriate SAE protocol specific reporting forms are completed and disseminated to the appropriate persons and within the designated timeframes as indicated above. For each AE/SAE recorded, the research staff will follow the AE/SAE until resolution, stabilization or until the subject is no longer in the study as stated in the protocol.

When a reportable SAE is identified, the Study Coordinator will initiate an SAE form, and the following individuals will be notified by facsimile transmission, email and/or telephone within 24-business hours of the initial notification of the SAE:

- i. The Principal Investigator and the Study Physician will provide oversight, consultation, assessment and documentation as appropriate of the SAE.
- ii. The research staff will notify the MUSC IRB and complete the AE report form in conjunction with the PI. The MUSC IRB meets monthly and is located at [name]. Communication with the IRB is through email, memos, official IRB forms, and online reporting.
- iii. The NIH program officer.
- iv. The DSMB members.

If complete information is not available when the initial 24-hour SAE report is disseminated, follow-up information will be gathered to enable a complete assessment and outcome of the event. This information may include hospital discharge records, autopsy reports, clinic records, etc. The research staff will attach copies of source documents to the SAE report for review by the PI and for forwarding to the NIH program officer as appropriate within 2 weeks of the initial SAE report. In addition, the PI will provide a signed, dated SAE summary report, which will be sent to the NIH Medical Safety Officer within two weeks of the initial SAE report.

We will report adverse events to the MUSC IRB online as soon as possible, but no later than 10 working days after the investigators first learn of the event. The MUSC IRB AE reporting requirements are as follows: All deaths that occur during the study or 30 days post termination from the study are required to be reported as adverse events even if they are expected or unrelated. Other adverse events are reportable to the MUSC IRB if the AE is unexpected AND related or possibly related AND serious or more prevalent than expected. All three criteria must be met for an AE to be reported to the MUSC IRB. The IRB definition of unexpected is that the AE is not identified in nature, severity or frequency in the current protocol, informed consent, investigator brochure or with other current risk information. The definition of related is that there is a reasonable possibility that the adverse event may have been caused by the drug, device or intervention. Reportable AEs are reviewed by the IRB Chair and reported to the IRB Board at the next meeting.

Trial Safety. The potential risks and benefits and methods to minimize these risks are outlined above. Protocols for reported AEs and SAEs are outlined above. All unexpected AE and SAEs will be monitored until resolved. A detailed summary of all AEs will be prepared weekly by the research staff. At the weekly

V5/11/2020

team meetings (or before if urgent), the research staff will report any premonitory symptoms of clinical deterioration.

Study procedures will follow as much as possible the FDA's Good Clinical Practice Guidelines (www.fda.gov/oc/gcp). Any outside requests for information or any breaches in confidentiality will be reported to the PI. All requests by subject's physicians and other medical providers will be referred directly to PI.

DSM Plan Administration. The PI will be responsible for monitoring the study. He will regularly (quarterly) examine the database for missing data, unexpected distributions or responses, and outliers. A DSM report will be filed with the IRB on a yearly basis, unless greater than expected problems occur. The report will include subject characteristics, retention and disposition of study subjects, quality assurance issues and reports of AEs, significant/unexpected AEs and serious AEs. We will report results at the end of the trial.

DSM Board. We will create a DSMB to monitor the overall participant safety, the rate and severity of adverse events, and the validity and integrity of the data. The panel includes 3 researchers with experience in treating patients with chronic pain, substance use disorders, opioid use disorders and/or Veteran populations ([name]; [name]; [name], DO). The board may be called at any point if needed for unexpected AEs, etc. Modification will be made in the procedures and/or the protocol if necessary based on the recommendations of the board.

Confidentiality will be maintained during all phases of the trial including monitoring, preparation of interim results, review, and response to monitoring recommendations.

ClinicalTrials.gov Requirements

In accordance with Public Law 110-85, the proposed trial will be registered with ClinicalTrials.gov. Applicable requirements regarding results reporting will be adhered to.

Inclusion of Women and Minorities

Both male and female subjects will be recruited. There will be no exclusion based on race or ethnicity. Subjects will be recruited without preference for gender, race, ethnicity or socio-economic status. Based on our previous VA data and ongoing RCTs with Veterans, we estimate that approximately 40% of the sample will be comprised of African Americans. We also will include female subjects; however, the percentage of female subjects in our catchment area is low (<8%). Thus, we do not anticipate a large number of female subjects (5%).

Inclusion of Children

The age range for the study is 18-70 years.

Literature Cited

1. Gironda, R.J., M.E. Clark, J.P. Massengale, and R.L. Walker, Pain among veterans of Operations Enduring Freedom and Iraqi Freedom. *Pain Med*, 2006. 7(4): p. 339-343. pmc-id:

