Randomization: We will stratify randomization by (1) severity of opiate use (COMM score) and (2) pain severity (BPI score). Urn randomization will be used to balance the randomization assignment with respect to these strata. The purpose of stratification is to distribute these potential prognostic factors equally across treatment groups.

Intent-to-Treat Analyses. All analyses will be performed on two samples: (1) the intent-to-treat sample consisting of all randomized subjects and (2) the completers sample consisting of all subjects who complete at least 7 out of 11 sessions.

Missing Data. We will perform attrition analyses on whether participants and dropouts differ on key variables (symptom severity) and whether variables on which they differ interact with treatments to affect outcome measures. As participants will be randomized to treatment, it is unlikely that missing data will produce biased estimates of treatment effect, as observed and unobserved covariates should theoretically be balanced across treatment groups. In addition, in general, less than 10% missing data have little impact upon study power and do not introduce bias, regardless of the missing data mechanism.⁷⁴ Larger proportions of data missing at random (MAR) or missing not at random (MNAR) could potentially bias study findings and reduce power. If the percent missing data are greater than 10%, propensity score methods will be used for data imputation. In the propensity score method, first the distribution of the missing indicator variable given the observed data is modeled to derive a propensity score. Then observations are grouped on these propensity scores and an approximate Bayesian bootstrap imputation is applied to each group.

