Time-Series Variables: The actigraphy devices will yield time-series data including sleep latency, total sleep time and sleep efficiency. Hierarchical Linear Modeling (HLM) will be applied to evaluate daily (time-series) pain, craving, opiate used, mood, anxiety, and physical activity ratings throughout the 3 phases of the study (baseline, treatment, and follow-up) and by group. The covariance structure of the model will be set to first-order autoregressive and independent effects of treatment on average daily pain will be assessed by controlling for daily fluctuations in craving, mood, anxiety, and activity in the model. Additional co-variates of CBT-related effects will include therapeutic alliance and pain coping styles. Additionally, cross-lag correlational analyses will be conducted on pain, craving, mood, anxiety, and activity data to estimate temporal order of changes during the trial.

Repeated Measures Variables: BPI, COMM, as well as mean weekly sleep latency, total sleep time and sleep efficiency scores will be examined with HLM using an unstructured covariance matrix. Subject-level intercepts will be entered into the model at level-1, and a time X group (real vs. sham tDCS) mixed model will be implemented. The primary model parameter of interest will be the time X group interaction term; however, main effects will be specified in the model. Effects of treatment on pain and opioid misuse will be separated from mood effects by co-varying mood and anxiety ratings at the individual subject-level.

Power: Effect sizes (Cohen's d) for CBT for chronic pain range from 0.3 to 1.4. A realistic effect-size estimate for the CBT intervention would be categorized as "medium/modest" (d=.5). The effect-size associated with clinical effects of tDCS on chronic pain in the current literature is also medium/modest (d=.5). With 150 subjects (75 in each group), power to detect effects (alpha=.05, effect-size d=.5, r among repeated measures=.5) is good to excellent (1- β = .80 and .99, respectively). Power will be higher for the HLM model as sources of intra-class variability are better managed.

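### The repeated-measures model tests time x group with arm means left free at baseline and no baseline adjustment, which gives up precision the trial could have at no data cost

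*Combined protocol and SAP*

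**What the plan says.** Under Randomization, the plan stratifies on COMM and BPI scores and uses an urn scheme: "Urn randomization will be used to balance the randomization assignment with respect to these strata". It gives the reason as "The purpose of stratification is to distribute these potential prognostic factors equally across treatment groups".

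Under Repeated Measures Variables (BPI, COMM and weekly mean sleep scores, unstructured covariance), the model is: "Subject-level intercepts will be entered into the model at level-1, and a time X group (real vs. sham tDCS) mixed model will be implemented". The target is: "The primary model parameter of interest will be the time X group interaction term; however, main effects will be specified in the model". The covariate sentence there reads "Effects of treatment on pain and opioid misuse will be separated from mood effects by co-varying mood and anxiety ratings at the individual subject-level". The Time-Series Variables paragraph adjusts daily pain for daily craving, mood, anxiety and activity, and adds: "Additional co-variates of CBT-related effects will include therapeutic alliance and pain coping styles". For daily data, baseline is one of three study phases of the outcome series.

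Hypotheses 1a, 1b, 2a and 2b refer back to these methods. Nowhere is the outcome's own baseline a covariate, are the arms constrained to a common baseline mean, or are the urn factors entered as covariates. The plan does not say whether time is categorical or linear, nor outright whether baseline is one of its levels.

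**The concern.** With a group main effect in the model, the arms may differ freely at baseline. If baseline is a level of categorical time, the time x group term at a visit is then the difference between arms in change from baseline. Randomisation makes the expected baseline means equal, and a model that uses this fact estimates the same treatment effect with smaller variance whenever r is below 1. The plan judged two baseline scores prognostic enough to balance on, yet its analysis draws little or no precision from them. At stake is power, chiefly where the margin is thin: the sleep outcomes, dropout, or a true effect below d=.5.

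**Working it through.** **Inputs from the documents.** Power paragraph: 75 per arm, d=.5, alpha .05, r=.5, stated power .80 and .99. Subjects section: actigraphy in about 90 participants. General Procedures: 2-week diary baseline. **Assumed:** two-sided tests (the power statement does not say), 45 per arm for sleep, and any r other than .5.

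**The plan's own figure.** A two-sample t test with 75 per arm at d=.5 has noncentrality .5 x √(75/2) = 3.06 and power .86, not .80. A value near .80 needs inputs the power statement does not give, such as 63 to 64 per arm or alpha .025. The .99 matches a within-arm paired test (n=75, standardised change .5/√(2(1-.5)) = .5; power .990). The .80 is a separate matter and does not affect what follows.

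**Variance of the treatment contrast**, in outcome SD², one baseline value and one post-baseline visit:
- free baseline, change contrast: 2(1-r); at r=.5 this is 1.00, the same as ignoring baseline altogether;
- baseline-adjusted or common baseline mean: 1-r²; at r=.5 this is .75.

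Power uses the noncentral t with noncentrality d/√v x √(n/2). At 75 per arm and r=.5, that is 3.06 against .5/√.75 x √37.5 = 3.54.

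| n per arm | r | as planned | adjusted |
|---|---|---|---|
| 75 | .3 | .73 | .89 |
| 75 | .5 | .86 | .94 |
| 75 | .7 | .975 | .989 |
| 45 (sleep) | .5 | .65 | .77 |
| 45 (sleep) | .7 | .86 | .91 |

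At r=.5, the adjusted analysis with 75 x .75 = about 56 per arm matches the planned one with 75. With an assumed 20% loss (60 per arm, r=.5), power is .78 against .88. With an assumed d=.4 at 75 per arm, it is .68 against .80.

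**Several visits.** Exact generalised least squares under compound symmetry, with 2 or 5 categorical time points at r=.5, gives the last-visit contrast a variance of .0267 as planned and .0200 with a common baseline mean, so the 25% reduction is unchanged. If the contrast averages four post-baseline visits, power is .972 against .999 (normal approximation). With linear time over 5 equally spaced visits, it is .928 against .977 (normal approximation).

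**Diary phase means.** Assume compound symmetry at daily r=.5, with 14 baseline and 77 treatment days. The phase-mean variances are .5+.5/14 = .5357 and .5+.5/77 = .5065, with covariance .5.
- Change: .5357 + .5065 - 1 = .0422.
- Adjusted: .5065 - .25/.5357 = .0398.

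The excess is about 6%, against 33% (1.00/.75) for a single visit. At r=.3 it is about 14%. The planned autoregressive structure would give other values.

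**Urn factors.** Adding a stratum as a main effect to the planned model leaves the time x group variance at .0267. It is constant within a person and cancels from the change. In a baseline-adjusted model, if the factors explain a further 2% to 10% of residual variance (assumed), power at 75 per arm and r=.5 rises from .942 to .946–.961 (normal approximation). Nearly all the gain therefore comes from the handling of baseline.

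**The case against.** A time x group mixed model is valid and standard. At the plan's own inputs it has power of about .86, above the lower stated figure of .80. Calling a constrained-baseline model an optional refinement is therefore fair at full sample size, and no claim of bias can be made. It is also fair that the single-visit figures do not carry over to every model: the gap is small at r=.7 or above with 75 per arm, and for long diary baselines. Weekly mean sleep scores may well correlate above .5.

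A reader might infer that leaving out the urn factors by itself inflates the standard error of the primary parameter. It does not, because that parameter is a within-person contrast. A reader might also infer that COMM and BPI play no part in the models. Both are outcomes, and each one's own baseline is presumably already the time-zero response. What is missing is the other factor in those two models, and both factors in the sleep and mood models.

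What stands is that, under the reading set out above, the planned contrast has larger variance than the adjusted one for every r below 1. If baseline is instead left out of the response, it is not used at all.

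**Conclusion.** The point holds as a loss of efficiency. At d=.5, r=.5 and 75 per arm, a single-visit contrast has power of about .86 as planned and .94 with baseline adjustment. For sleep, with 45 per arm and r=.5 assumed, it is about .65 against .77. These figures assume baseline is a level of categorical time, one baseline value against one post-baseline visit, two-sided testing and no dropout. The loss is smaller at higher r, with linear time, and for diary outcomes. The documents do not support a reading that the planned test is biased, or that it falls below .80 for pain and opioid misuse at the plan's own inputs. The change is worth making because sleep is listed among the primary outcomes in the data and safety monitoring plan, and because dropout or a smaller effect would use up the margin elsewhere.

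**What to change.** State in the SAP how time is coded and whether baseline is a response. Then, for each outcome, choose one of two models.

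- **(a)** Model post-baseline values only, with that outcome's baseline crossed with time, plus baseline COMM and baseline BPI each crossed with time. Where one of these is the outcome's own baseline, it enters once.
- **(b)** Keep baseline as a response, constrain the arms to a common baseline mean, and add only the urn factor or factors that are not that outcome's own baseline, crossed with post-baseline time.

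Do not enter the same baseline as both response and covariate; in the BPI and COMM models the baseline row would then predict itself. Do not add the urn factors to the unconstrained model as main effects only. Name the BPI score used in the urn, since randomisation refers to pain severity while Hypothesis 1a analyses the total score.

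The cost is SAP wording and model code. No new data are needed: COMM and BPI scores are already required for eligibility.

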Subjects will be dropped from the study and referred for more intensive treatment if there is: (1) increases in alcohol or drug use leading to the need for a more intensive level of care (i.e., medical detoxification, inpatient or partial hospitalization); (2) active suicidal or homicidal ideation; (3) inability to manage the subject psychiatrically within the inclusion/exclusion criteria of the study (i.e., need for the initiation of psychotropic medications; development of psychosis); or (4) inability to return for therapy appointments due to incarceration or hospitalization.

There is a well-established protocol at our site for emergency psychiatric evaluation, crisis intervention and/or psychiatric hospitalization for suicidal, homicidal, psychotic or other acutely distressed subjects. Immediately on detection of these needs, the assessor/therapist will page a psychiatrist to review the subject's situation. If appropriate, the psychiatrist will personally evaluate the subject. Alternatively, during weekdays, the subject will be escorted by a study staff member to the psychiatric walk-in clinic or emergency room. During evenings or weekends, the site PI or clinical staff will be on-call for emergencies. At these times, acutely distressed subjects will be instructed to go to the psychiatric emergency room for evaluation by the psychiatric resident. The on-call clinical psychologist or psychiatrist will have notified the resident in advance of the subject's situation. Psychiatric hospitalization is available for emergencies.

Suicide Specific Risk Identification and Response Plan

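### The Missing Data paragraph treats loss under 10% as free of bias whatever its cause; this fails for outcome-related loss that differs by arm, and the rule above 10% leaves the donor pool, the denominator and any MNAR check unstated

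*Combined protocol and SAP*

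**What the plan says.** Three statements in the Missing Data paragraph (Statistical Analyses and Power) matter here.

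- On randomisation: "As participants will be randomized to treatment, it is unlikely that missing data will produce biased estimates of treatment effect".
- On small amounts of loss: "in general, less than 10% missing data have little impact upon study power and do not introduce bias, regardless of the missing data mechanism".
- On large amounts: "Larger proportions of data missing at random (MAR) or missing not at random (MNAR) could potentially bias study findings and reduce power".

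The action rule follows: "If the percent missing data are greater than 10%, propensity score methods will be used for data imputation". A model for the missingness indicator given the observed data yields the score; then "observations are grouped on these propensity scores and an approximate Bayesian bootstrap imputation is applied to each group". Arm is neither named in nor excluded from that model, and no rule says which arm donors come from. The paragraph does not say what the 10% is a percentage of.

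Attrition analyses are planned at any level of loss. They compare dropouts with participants on key variables and ask whether those variables interact with treatment. No MNAR sensitivity analysis and no expected dropout rate appear.

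Under Repeated Measures Variables, "a time X group (real vs. sham tDCS) mixed model will be implemented" for BPI, COMM and the weekly sleep scores, with unstructured covariance and with adjustment by "co-varying mood and anxiety ratings at the individual subject-level". The Safety and Monitoring Plan adds a source of loss: "Subjects will be dropped from the study and referred for more intensive treatment" on grounds that include substance use needing a higher level of care and the need to start psychotropic medication.

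**The concern.** Randomisation makes the arms comparable at baseline. It says nothing about the subjects who still have data at the end, because leaving can depend on treatment and on outcome. The clause on the mechanism extends the no-bias claim to MNAR loss, which is the case in which it can fail.

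Below 10%, the mixed model already handles MAR loss given what it models. The gap is that the plan's wording would let MNAR loss be declared harmless without a check. Above 10%, the plan moves to an imputation that, on one reading, fills gaps in one arm with outcomes from the other and so shrinks a true effect. The plan concedes that MNAR loss can bias findings at that level but provides no analysis that shows by how much.

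**Working it through.** **Inputs.** From the Power paragraph: 75 per arm, alpha .05 (two-sided assumed), d = .5, r = .5. Assumed: all loss patterns, because the documents give no dropout rate. Higher scores are worse, the SD is 1, and the true effect is -0.50 or 0.

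**1. The plan's own figures.** The 10% rule is asserted, so there is no calculation to reproduce. The nearest figure is power: Φ(0.5·√(75/2) − 1.96) = Φ(1.10) = 0.86. The same holds for change from baseline, since √(2(1 − .5)) = 1. The stated .80 is not reproduced; it fits about 63 to 64 per arm, and it does not bear on this point. With 10% lost (67.5 per arm), Φ(0.5·√(67.5/2) − 1.96) = Φ(0.95) = 0.83. The power half of the sentence is therefore roughly fair, and the bias half is what is in question.

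**2. Below 10%, loss relative to the arm mean.** Take one baseline and one outcome. If a fraction q of an arm is lost and the lost subjects are g SD worse than their arm mean, the observed mean shifts by q·g/(1 − q). A likelihood analysis that uses baseline removes the share r² and leaves 1 − r² = 0.75. The bias in the effect is the difference between the arms in 0.75·q·g/(1 − q). With log-odds of loss rising by 1 per SD, g is 0.88, 0.83, 0.78 and 0.71 at q = 6.2%, 9.3%, 12.4% and 18.6%. All rows have 9.3% missing overall; type I error is from simulation (8,000 trials per pattern).

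| Pattern | Arithmetic | Bias (SD) | Type I error |
|---|---|---|---|
| Same process in both arms | 0.064 − 0.064 | 0.00 | 0.05 |
| 12.4% v 6.2% | 0.083 − 0.043 | 0.04 | 0.06 |
| Outcome-driven in one arm, random in the other | 0.064 − 0 | 0.06 | 0.06-0.07 |
| All loss in one arm (18.6% v 0) | 0.121 − 0 | 0.12 | 0.10 |

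The direction depends on which arm is affected. The simulated biases agree with the arithmetic.

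**3. Below 10%, one absolute rule for both arms.** If treatment works, fewer real-arm subjects meet the rule. The estimate is about -0.50 + 0.75 × (sham shift − real shift).

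| Rule | Lost, sham v real | Arithmetic | Simulated | Power |
|---|---|---|---|---|
| Graded risk, logit⁻¹(-2.42 + score) | 11.2% v 7.4% | -0.50 + 0.75(0.101 − 0.069) = -0.48 | -0.48 | 0.80 |
| Half of those above 0.67 leave | 12.6% v 6.0% | -0.50 + 0.75(0.182 − 0.107) = -0.44 | -0.44 | 0.75 |
| All above 1.11 leave | 13.4% v 5.4% | -0.50 + 0.75(0.249 − 0.115) = -0.40 | -0.39 | 0.65 |

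With no treatment effect the two shifts cancel: there is no bias, and type I error is 0.05.

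**4. Effect of repeated measures.** The plan has weekly measures, which carry information about a subject before loss. With ten intermediate waves, all observed, and only the final value lost, the third row in step 2 falls from about 0.06 SD to 0.044-0.046 (all correlations .5) or 0.022-0.027 (adjacent waves about 0.82). The one-arm case falls from 0.12 to 0.09 or 0.05. The strictest rule in step 3 moves from -0.39 to -0.42 or -0.45. Earlier dropout would lie in between.

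**5. Above 10%, MAR loss.** If a fraction m is filled from donors pooled across arms, the effect shrinks to about 0.50 × (1 − m). The simulation used five propensity groups and a propensity model with arm and baseline. It also assumed ten imputations combined by Rubin's rules; the plan states neither.

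| Missing | 0.50 × (1 − m) | Pooled (power) | Within arm (power) | Likelihood power |
|---|---|---|---|---|
| 15% | 0.43 | -0.43 (0.68) | about -0.50 (0.79) | 0.81 |
| 24% | 0.38 | -0.39 (0.56) | about -0.50 (0.76) | 0.79 |
| 30% | 0.35 | -0.35 (0.43) | about -0.50 (0.70) | 0.75 |
| 38% | 0.31 | -0.32 (0.34) | about -0.50 (0.64) | 0.70 |

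Within-arm and likelihood estimates lie between -0.49 and -0.51. Rejection under the null is 0.02-0.03 pooled, 0.05-0.06 within arm and 0.04-0.05 for likelihood. Putting arm in the propensity model is not enough. In a separate run with loss unrelated to outcome at 15%, 20% and 30%, the 0.50 effect became 0.46, 0.44 and 0.41 with arm as a covariate, and stayed at 0.50 with donors within arm.

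**6. Above 10%, MNAR loss.** At 22%, outcome-driven in one arm and random in the other, the estimate depends on the arm affected: likelihood -0.65 or -0.36, within-arm bootstrap -0.66 or -0.35 with type I error 0.13-0.14. A shift of +0.75 SD in the affected arm brings the within-arm result to -0.49 or -0.52 and type I error to 0.05.

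**7. The trigger.** Suppose 14% of subjects (assumed) are lost evenly over K assessments. Then 14% are missing at the last one, but the share of records is 14% × (K + 1)/(2K): 9.3% at K = 3, 8.8% at K = 4 and 7.5% at K = 15. The same loss falls on either side of 10%.

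**The case against.** The plan's sentences are hedged: one speaks in general, the other says unlikely. Outside the one-arm extreme, the bias below 10% is a few hundredths of an SD, and it is smaller still once weekly measures enter the model. A single rule applied to both arms costs only power. The attrition analyses look for differential loss. Pooled donors are one reading of a silent text. All of this stands, and it limits the size of the point. It does not make the claim about the mechanism true, and an attrition screen corrects no estimate.

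Three stronger readings are tempting, and the documents do not support them.

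- A reader might infer that the plan mixes the arms when it imputes. It does not say so; it omits the rule.
- A reader might infer that the Safety and Monitoring Plan removes subjects for worsening pain. Its grounds are not pain scores. They make outcome-related loss foreseeable mainly for opioid and other substance use outcomes. Subjects who drop out of treatment may still give follow-up data, since remote completion on REDCap is allowed.
- A reader might infer large false-positive inflation. Losing exactly the worst 15% of one arm and the worst 3% of the other (9% overall), with no use of earlier values, would give 0.20 SD and type I error of about 0.22. Nothing in the documents points to loss that sharp, and the planned model does use earlier values.

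**Conclusion.** The two no-bias statements are wrong for MNAR loss that differs by arm. Bias is zero if loss depends equally in both arms on outcome relative to the arm mean, or if one absolute rule applies and treatment has no effect. If treatment works, one absolute rule shrinks the effect without raising type I error.

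At about 9% missing, the two-wave figures of 0.04 to 0.06 SD, and 0.12 SD with all loss in one arm, are upper-end values for the assumed patterns; the mixed model would reduce them. Above 10%, the open donor rule decides between essentially no MAR bias and a loss of 14% to 36% of a true effect (0.07/0.50 to 0.18/0.50), on the conservative side. Which branch applies is unknown, because no dropout rate is given and the 10% has no denominator. The point should be fixed. It does not show that the trial's result will be biased.

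**What to change.** - Delete the two no-bias statements and the 10% trigger.
- Make the mixed model on all observed data of all randomised subjects primary at any missing fraction, and state that it assumes MAR. Below 10% this is in substance the existing plan.
- Where imputation is used, for example for missing mood and anxiety covariates, impute within arm. If the propensity and bootstrap step is kept, restrict donors to the same arm and say what the 10% is a percentage of.
- Add a pre-specified delta-adjusted (tipping-point) MNAR sensitivity analysis with arm-specific shifts in both directions, and report the shift at which the conclusion changes.

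The cost is SAP wording and a few extra model runs. The range of shifts must be fixed before unblinding. Data collection does not change.
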